^δ FNAIT testing and RLYB212 specific tests are performed in central laboratories; all other tests are performed locally.

10.3 Appendix 3: Adverse Events: Definitions and Procedures for Recording, Evaluating, Follow-up, and Reporting

10.3.1 *Definition of Adverse Events*

AE Definition

An AE is any untoward medical occurrence in a patient or clinical study participant, temporally associated with the use of study intervention, whether or not considered related to the study intervention. NOTE: An AE can therefore be any unfavorable and unintended sign (including an abnormal laboratory finding), symptom, or disease (new or exacerbated) temporally associated with the use of study intervention.

Events Meeting the AE Definition

Any abnormal laboratory test results (hematology, clinical chemistry, or urinalysis) or other safety assessments (eg, ECG, radiological scans, vital signs measurements), including those that worsen from baseline, considered clinically significant in the medical and scientific judgment of the investigator (ie, not related to progression of underlying disease).Exacerbation of a chronic or intermittent pre-existing condition including either an increase in frequency and/or intensity of the condition.New conditions detected or diagnosed after study intervention administration even though it may have been present before the start of the study.Signs, symptoms, or the clinical sequelae of a suspected drug-drug interaction.Signs, symptoms, or the clinical sequelae of a suspected overdose of either study intervention or a concomitant medication. Overdose per se will not be reported as an AE/SAE unless it is an intentional overdose taken with possible suicidal/self-harming intent. Such overdoses should be reported regardless of sequelae.For efficacy studies, “lack of efficacy” or “failure of expected pharmacological action” per se will not be reported as an AE or SAE. Such instances will be captured in the efficacy assessments. However, the signs, symptoms, and/or clinical sequelae resulting from lack of efficacy will be reported as AE or SAE if they fulfil the definition of an AE or SAE.

Events NOT Meeting the AE Definition

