4.2.2.4. Maternal Clinical Laboratory Values

Summaries for safety laboratory will be presented for the SAS, which will only include the parameters specified in [Table 5](#).

All values will be classified as low (below range), normal (within range), or high (above range) based on laboratory reference ranges. Results will be presented in PAREXEL standard units as specified in [Table 6](#) and all the clinical laboratory parameter values in collected lab units will be converted to PAREXEL standard units using the corresponding conversion factors as shown in [Table 7](#). For all continuous laboratory assessments, absolute value, will be summarized using descriptive statistics at each scheduled assessment timepoint.

If the same parameter is found as measured in serum and in plasma, then the summaries will not distinguish between them (e.g. values from plasma albumin and serum albumin will be summarized under albumin). If the same parameter is found as measured in serum and in plasma

for the same participant (which would be a rare case), then the change from baseline will only be calculated for those post-baseline values using the same source, i.e., only within plasma or serum.

For clinical chemistry, hematology and coagulation, shift tables will be presented from baseline to worst value on-treatment (defined from start of treatment to parturition) according to reference range classification (HIGH, LOW, NORMAL). A shift table from baseline to maximum value will be summarized for urine dipstick variables.

Spaghetti plots of absolute values for all hematology, coagulation and clinical chemistry parameters will also be presented.

Liver biochemistry test results over time for participants who show elevated ALT or AST ($\geq 3 \times$ ULN) and elevated bilirubin ($\geq 2 \times$ ULN) (elevated results do not need to be present at the same visit) or ALT or AST of $\geq 5 \times$ ULN, will be tabulated and plotted. Plots for both maximum post-baseline alanine transaminase (ALT) and aspartate transaminase (AST) versus the maximum post-baseline total bilirubin (expressed as multiples of their upper limit of normal [ULN] reference range) will be produced with reference lines at 3 x ULN for ALT and AST and 2 x ULN for total bilirubin (eDISH plot).

All laboratory results collected will be listed.

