Lymphocytes (ABS)	LYMPABS	10 ⁶ /L	0.00100	10 ⁹ /L
Lymphocytes (ABS)	LYMPABS	/µL	0.00100	10 ⁹ /L
Lymphocytes (ABS)	LYMPABS	k/µL	1.00000	10 ⁹ /L
Lymphocytes (ABS)	LYMPABS	10 ³ /µL	1.00000	10 ⁹ /L
Lymphocytes (ABS)	LYMPABS	10 ³ /mm ³	1.00000	10 ⁹ /L
Lymphocytes (ABS)	LYMPABS	10 ⁹ /L	1.00000	10 ⁹ /L
Lymphocytes (ABS)	LYMPABS	/nL	1.00000	10 ⁹ /L
Mean Corpuscular Hemoglobin (MCH)	MCH	pg	1.000	pg
Mean Corpuscular Hemoglobin (MCH)	MCH	µµg	1.000	pg
Mean Corpuscular Hemoglobin (MCH)	MCH	amol	0.065	pg
Mean Corpuscular Hemoglobin (MCH)	MCH	amolFe	0.016	pg
Mean Corpuscular Hemoglobin (MCH)	MCH	fmol	16.114	pg
Mean Corpuscular Hemoglobin (MCH)	MCH	fmolFe	16.250	pg
Mean Corpuscular Hemoglobin Concentration (MCHC)	MCHC	mmol/L	16.114	g/L

Project Document Version No.:2.0; Document Effective Date: Date of last signature

TP-GDO-WW-016-09

Effective Date: 22 Dec 21

Related to: SOP-GDO-WW-019

Page 63 of 70

Parexel International

Rallybio IPA, LLC
IPA2202

Statistical Analysis Plan

LAB TEST DESCRIPTION (SDTM Labtest)	QUESTION	Collected Unit	Conversion Factor	PAREXEL Standard Unit for Presentation
Mean Corpuscular Hemoglobin Concentration (MCHC)	MCHC	%	10.000	g/L
Mean Corpuscular Hemoglobin Concentration (MCHC)	MCHC	g/dL	10.000	g/L
Mean Corpuscular Hemoglobin Concentration (MCHC)	MCHC	g%	10.000	g/L
Mean Corpuscular Hemoglobin Concentration (MCHC)	MCHC	g/L	1.000	g/L
Mean Corpuscular Volume (MCV)	MCV	fL	1.00000	fL
Mean Corpuscular Volume (MCV)	MCV	µm ³	1.00000	fL
Monocytes (REL)	MONO%	%	1.00000	%
Monocytes (REL)	MONO%	Proportion of 1.0	100.00000	%
Monocytes (REL)	MONO%	Fraction	100.00000	%
Monocytes (ABS)	MONOABS	Giga/L	1.00000	10 ⁹ /L
Monocytes (ABS)	MONOABS	/cumm	0.00100	10 ⁹ /L
Monocytes (ABS)	MONOABS	/mm ³	0.00100	10 ⁹ /L
Monocytes (ABS)	MONOABS	10 ⁶ /L	0.00100	10 ⁹ /L
Monocytes (ABS)	MONOABS	/µL	0.00100	10 ⁹ /L
Monocytes (ABS)	MONOABS	k/uL	1.00000	10 ⁹ /L
Monocytes (ABS)	MONOABS	10 ³ /µL	1.00000	10 ⁹ /L
Monocytes (ABS)	MONOABS	10 ³ /mm ³	1.00000	10 ⁹ /L
Monocytes (ABS)	MONOABS	10 ⁹ /L	1.00000	10 ⁹ /L

Project Document Version No.:2.0; Document Effective Date: Date of last signature

TP-GDO-WW-016-09

Effective Date: 22 Dec 21

Related to: SOP-GDO-WW-019

Page 64 of 70

Parexel International

Rallybio IPA, LLC
IPA2202

Statistical Analysis Plan

LAB TEST DESCRIPTION (SDTM Labtest)	QUESTION	Collected Unit	Conversion Factor	PAREXEL Standard Unit for Presentation
Monocytes (ABS)	MONOABS	/nL	1.00000	10 ⁹ /L
Monocytes (ABS)	MONOABS	Gpt/L	1.00000	10 ⁹ /L

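### SAP Table 7: the plain amol and fmol factors for MCH disagree about 4-fold, so they cannot share one molecular basis, and the SAP does not say which basis is meant

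*SAP*

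**What the plan says.** SAP 4.2.2.4 presents laboratory results in the CRO's standard units. Anything a laboratory reports differently "will be converted to PAREXEL standard units using the corresponding conversion factors as shown in" an appendix table, namely Table 7 in SAP 6.3 (Appendix 3). Four rows of that table carry the label "Mean Corpuscular Hemoglobin (MCH" and start from a molar unit:

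- The plain attomole row is "Mean Corpuscular Hemoglobin (MCH) MCH amol 0.065 pg".
- The attomole row with the Fe suffix is "Mean Corpuscular Hemoglobin (MCH) MCH amolFe 0.016 pg".
- The plain femtomole row is "Mean Corpuscular Hemoglobin (MCH) MCH fmol 16.114 pg".
- The femtomole row with the Fe suffix is "Mean Corpuscular Hemoglobin (MCH) MCH fmolFe 16.250 pg".

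For the concentration measure, the only molar row is "Mean Corpuscular Hemoglobin Concentration (MCHC) MCHC mmol/L 16.114 g/L". Hemoglobin in mmol/L has a different factor, 16.049.

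MCH is a required hematology parameter (Protocol Table 10-1, SAP Table 5). Hematology does not go to the central laboratories: apart from FNAIT and RLYB212-specific testing, "all other tests are performed locally" (Protocol Appendix 2). SAP 4.9, added after early termination, replaces all tables and figures with participant-level listings. Laboratory results are among the listings it keeps, and it records that one participant was enrolled.

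**The concern.** Two rows for one analyte, differing only in a metric prefix, must have factors exactly 1,000 apart. The plain MCH rows are about 248 apart (16.114/0.065). The same measurement would therefore convert to two values roughly 4-fold apart, depending on which prefix the laboratory used.

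The entry still matters because Table 7 is the operative conversion rule and the laboratory listing survives the reduction in SAP 4.9. With summaries, shift tables and plots dropped, no second output would show up a misconverted value. MCH is also collected in local laboratories, so the SAP does not control the collected unit.

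**Working it through.** **Inputs** (SAP Table 7, factors to pg): amol 0.065; amolFe 0.016; fmol 16.114; fmolFe 16.250. The only outside fact is the metric prefix, 1 fmol = 1,000 amol.

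**Rule.** On one molecular basis, amol factor = fmol factor / 1,000.

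| Pair | fmol factor / 1,000 | Printed amol factor | Printed / implied |
|---|---|---|---|
| Fe rows | 16.250/1,000 = 0.01625 | 0.016 | 0.985 (-1.5%, rounding to three decimals) |
| Plain rows | 16.114/1,000 = 0.016114 | 0.065 | 4.03 |

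The Fe pair passes and the plain pair fails.

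**Can 0.065 be reproduced another way?** Yes. If the plain unit counts whole hemoglobin molecules with four irons each, the factor is 4 x 16.250/1,000 = 0.0650, which is the printed value. On that basis, though, the plain fmol factor would have to be 0.065 x 1,000 = 65, not 16.114.

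**Plain row against Fe row, by prefix**

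- Attomoles: 0.065/0.016 = 4.06, which suggests a four-iron plain unit.
- Femtomoles: 16.114/16.250 = 0.99, which suggests a one-iron plain unit.

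The table treats the plain unit as two different things. The conflict remains whichever reading is chosen.

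**Size for one cell, under each reading**

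- If the fmol row is right: 30 pg is 30/16.114 = 1.862 fmol = 1,862 amol, and the amol row returns 1,862 x 0.065 = 121 pg.
- If the amol row is right: 30 pg is 30/0.065 = 461.5 amol = 0.4615 fmol, and the fmol row returns 0.4615 x 16.114 = 7.4 pg.

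**Two smaller gaps in Table 7, for completeness**

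- Hemoglobin and MCHC in mmol/L: 16.114/16.049 = 1.004, a gap of 0.4%. At 7.5 mmol/L this is 120.9 against 120.4 g/L.
- Glucose: 5.55060 per g/L implies 5.55060/100 = 0.055506 per mg/dL. The printed 0.056 is that figure rounded, and 0.056/0.055506 = 1.009, a gap of 0.9%. At 100 mg/dL this is 5.60 against 5.55 mmol/L. The mg/dL, mg% and mg/L rows agree with one another.

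**The case against.** The strongest reply is that 0.065 may be no mistake. The table lists amol and amolFe separately, and a ratio of about 4 between them is what a whole-molecule unit and a per-iron unit should show. A reader might infer that the amol row is four times too high and that a normal cell would be listed at 121 pg. The documents do not support that: the figure assumes that the fmol row is the correct one, and the opposite assumption gives 7.4 pg from the fmol row instead. This stands, and it also means that changing 0.065 to 0.0161 without checking could create an error for a laboratory that reports per four-iron molecule. It does not reconcile the rows, because the fmol row would then be the one off basis.

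A reader might also infer that hemoglobin, MCHC and glucose show the same fault. They do not. The glucose gap is rounding of the factor. The hemoglobin and MCHC factors apply to two analytes with one mmol/L row each, and SAP 4.2.2.4 does not derive one from the other. Both are tidying points.

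Finally, a reader might expect listed values to vary between sites. With one participant enrolled and no summaries planned, that is largely moot. No document says that any laboratory reports MCH in amol or fmol. The low, normal and high classes in SAP 4.2.2.4 rest on laboratory reference ranges, so they do not change if value and range are converted with the same factor. All of this limits the consequence; it does not make the two plain rows agree.

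**Conclusion.** The plain amol and fmol rows for MCH in SAP Table 7 are inconsistent by a factor of 4.03 and cannot both be right on any single molecular basis. The documents do not show which row is off, so the conclusion is about the pair.

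The point is of low severity. At most it affects MCH in the laboratory listing of the one enrolled participant. The roughly 4-fold error arises only if MCH was reported in the plain molar unit whose factor is on the wrong basis for that laboratory. If MCH was reported in pg, the factor is 1.000 and nothing changes. The conclusion also assumes that the listing shows converted values, as SAP 4.2.2.4 implies; SAP 4.9 does not restate the unit.

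**What to change.** 1. Confirm with the laboratory that measured the participant's MCH which unit it reports and, if a plain molar unit, on which molecular basis.
2. Put both plain MCH rows in Table 7 on that one basis, state it, and keep the amol factor at the fmol factor divided by 1,000: either 0.0161 with 16.114 (one-iron), or 0.065 with about 65 (four-iron).
3. Optional tidying in the same edit: use one mmol/L factor for hemoglobin and MCHC, and carry another digit for glucose (0.0555 per mg/dL and per mg%, 0.00555 per mg/L).

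The cost is one changed table entry, a short note on the basis and one query to a laboratory, plus a few more entries if the tidying is done. No new data are needed, and the MCH listing needs to be rerun only if a plain molar unit was in fact collected.
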